4.14.2.1 Sensitivity Analysis; patients with FN and FP results

The primary efficacy analysis will be repeated with a reclassification of patients with one FN and one FP region. In particular, in the sensitivity analysis, these patients will be classified as FN. The results will be displayed in a summary of frequency of PET Patient level Classifications including estimates and CI of Sensitivity and Specificity according to each blinded reader. Frequencies will be displayed in a bar chart. Sensitivity and Specificity will be plotted for each reader including CI and performance goals.

4.14.3 Secondary Efficacy Variables

All secondary efficacy variables will be analyzed descriptively, with the exception of item 7; Kappa statistic.

Patient pathway through the study (PET scan, M0/M1, subsequent RP-PLND (Yes/No) and additional steps will be summarized and listed.

The following items are presented per secondary efficacy variable.

4.14.3.1 Percentage of patients in whom rhPSMA-7.3 (¹⁸F) imaging detects at least one verified M1 metastasis, as determined by central BIE.

This analysis concerns patients in the EEP with rhPSMA-7.3 (¹⁸F) imaging and confirmation tested (biopsy or additional imaging).

The percentage of patients with at least one M1 metastasis will be provided for each blinded independent reader. M1 metastasis requires the reader to identify a positive lesion in one of the three following locations: lymph nodes outside the pelvis, soft tissue/parenchyma or the bones. Patients will be counted to have M1 metastasis for this variable if a BIE detects M1 on the rhPSMA-7.3 (¹⁸F) and M1 is confirmed (biopsy, additional imaging) at the same location.

Patients where M1 was not verified (e.g. because the local reader did not detect M1) will be included in this analysis, as long as the BIE reader has detected M1 – in this case, the patients' metastasis will be considered as not verified. An additional table will be made using the EEP to summarize for each blinded reader the number of patients who have M1 by BIE and the presence / absence of confirmation of M1 metastasis.

PAREXEL International

Blue Earth Diagnostics
BED-PSMA-301

Statistical Analysis Plan

The endpoint for the secondary objective 1 of Verified Detection Rate (VDR) for M1 disease on a patient level is the percentage of patients with True-Positive M1 disease in the EEP.

$$VDR = (TP)/(TP+FP+TN+FN)$$

where:

- TP = BIE PET positive and SoT positive
- FP = either: (1) BIE PET positive and SoT negative or (2) BIE PET positive and SoT not done or not proven (NB: If site PET = M0, we would still have baseline imaging and so will count in SoT)
- FN = BIE PET negative and SoT positive
- TN = either: (1) BIE PET negative and SoT negative or (2) BIE PET negative and SoT not done

Results for M1 detections by central, blinded readers will be reported overall and by SOT method used (histopathology, and imaging only) to confirm M1 detection as True Positive or False Positive.

4.14.3.2 Percentage of patients with negative conventional imaging for M1 disease in whom rhPSMA-7.3 (¹⁸F) PET detects at least one verified M1 metastasis, as determined by central BIE.

This analysis concerns patients in the EEP with rhPSMA-7.3 (¹⁸F) imaging and confirmation tested (biopsy or additional imaging) and with conventional imaging yielding negative M1 disease.

The patients counted in this variable are a subset of 'Percentage of patients in whom rhPSMA-7.3 (¹⁸F) imaging detects at least one verified M1 metastasis, as determined by central BIE', where both the numerator and denominator are only counting patients with negative conventional imaging (according to investigator assessment) for M1 disease.

The endpoint for the secondary objective 2 of Verified Detection Rate (VDR) for M1 disease on a patient level with negative conventional imaging is the percentage of patients with negative conventional imaging (according to investigator assessment) for M1 disease and with True-Positive M1 disease according to rhPSMA-7.3 (¹⁸F) PET in the EEP.

4.14.3.3 Patient level PPV of rhPSMA-7.3 (¹⁸F) PET BIE for N1 and M1 lesions compared to histopathology or confirmatory imaging (M1 lesions only).

This analysis concerns EEP patients with rhPSMA-7.3 (¹⁸F) imaging and either N1 or M1 lesions detected.

PPV of N1 lesions is the proportion of patients with a positive PET BIE finding in pelvic lymph nodes and confirmed by histopathology, out of the patients with a positive PET BIE finding in pelvic lymph nodes.

PPV of M1 lesions is the proportion of patients with a positive PET BIE finding in other (extra-pelvic) areas and confirmed by SoT (histopathology or confirmatory imaging (as determined by central SoT)), out of the patients with a positive PET BIE finding in other (extra-pelvic) areas.

PAREXEL International

Blue Earth Diagnostics
BED-PSMA-301

Statistical Analysis Plan

4.14.3.4 PPV of rhPSMA-7.3 (¹⁸F) PET for detecting pelvic LN metastases compared to surgical pathology on a patient level in which a FP patient is defined as having at least one FP region (right or left pelvis), regardless of any coexisting TP findings.

This analysis concerns patients in the EAP where rhPSMA-7.3 (¹⁸F) imaging detected pelvic LN metastasis. Regions where rhPSMA-7.3 (¹⁸F) imaging detected no LN metastasis are not part of this by definition of PPV, hence only TP and FP regions will be taken into account.

PPV = TP / (TP + FP)

True positives will be all patients with a surgical pathology confirmed positive region and without a false positive region. False Positive patients will be those patients with any rhPSMA-7.3 (¹⁸F) PET positive region with negative surgical pathology or no surgical pathology.

4.14.3.5 NPV of rhPSMA-7.3 (¹⁸F) PET for detecting pelvic LN metastases compared to surgical pathology on a patient level in which a FN patient is defined as having at least one FN region (right or left pelvis), regardless of any coexisting TN findings.

This analysis concerns patients in the EAP with rhPSMA-7.3 (¹⁸F) imaging, where no LN metastases were detected and LN surgical pathology is available.

Regions where rhPSMA-7.3 (¹⁸F) imaging detected positive LN are not part of this by definition of NPV, hence only TN and FN regions will be taken into account.

NPV = TN / (TN + FN)

True negatives will be all patients with a surgical pathology confirmed negative region and without a false negative region. False negative patients will be those patients with any rhPSMA-7.3 (¹⁸F) PET negative region with positive surgical pathology.

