4.12 Standard of Truth

Histology or confirmatory imaging will be used as the Standard of Truth (SoT), as defined below.

1. Histology
 - a. Histology of surgically removed pelvic LNs;
 - b. Histology obtained by biopsy of M1 lesion.
2. Confirmatory Imaging
 - a. In patients without available histopathology, confirmatory conventional imaging is acceptable as proof of M1 disease in case of unequivocal findings (e.g. sclerotic bone lesions on CT, positive bone lesions on bone scan, evidently enlarged LNs radiologically considered metastases, lesions in the liver representing metastases as determined by ultrasound, CT or MRI, multiple pulmonary nodules on CT).

PAREXEL International

Blue Earth Diagnostics
BED-PSMA-301

Statistical Analysis Plan

b. Confirmatory imaging for proof of M1 disease will be read centrally. Three central reviewers will review all submitted imaging and reach consensus on the nature of the target lesion. Reads of the confirmatory imaging as SoT will be directed by rhPSMA-7.3 (¹⁸F) PET findings (for confirmation of lesion location only). A brief summary of clinical information will be available to the SoT readers (e.g. 67-year-old male with newly diagnosed, localized prostate cancer prior to rhPSMA-7.3 (¹⁸F) scan). Readers will be blinded to all other information. Further details are given in the study Independent Review Charter.

3. Baseline Conventional Imaging only

a. If M1 lesion identified by blinded PET reader but not site reader, or if M1 lesion is identified by site reader but no histology or no confirmatory imaging is available, then only conventional imaging at baseline will be used to determine the SoT.

SoT will be listed next to the results of the blinded independent reads and include method (Histology/Confirmatory Imaging/Baseline Imaging only), anatomical location and Result(s) using the EEP. Histology SoT will be assessed based on local reads of the PET scan, and these results will be included irrespective of BIE reading. The SoT will be summarized by method and anatomical location.

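### SAP 4.14.3.1 and 4.14.3.2 give conflicting analysis sets for the M1 Verified Detection Rate: the lead-ins keep only patients with confirmatory testing, while the formula counts patients with no Standard of Truth

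*SAP*

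**What the plan says.** **SAP 4.14.3.1 (secondary endpoint 1)** makes four statements about who is counted.

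- The lead-in takes EEP patients with "imaging and confirmation tested (biopsy or additional imaging".
- The numerator sentence counts an M1 call by blinded image evaluation (BIE) only if it is confirmed at the same location. It names biopsy and additional imaging as the means.
- The next paragraph keeps patients whose M1 was not verified, on condition that the blinded reader called M1, and treats the lesion as unverified.
- The endpoint definition says that the VDR "on a patient level is the percentage of patients with True-Positive M1 disease in the EEP", computed as TP/(TP+FP+TN+FN). The FP cell includes "BIE PET positive and SoT not done or not proven", with the note "If site PET = M0, we would still have baseline imaging and so will count in SoT". The TN cell includes "BIE PET negative and SoT not done".

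**SAP 4.14.3.2 (endpoint 2)** opens with patients with PET "and confirmation tested (biopsy or additional imaging) and with conventional imaging yielding negative M1 disease". It then describes a subset of endpoint 1 "where both the numerator and denominator are only counting patients with negative conventional imaging (according to investigator assessment) for M1 disease".

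**SAP 4.12 item 3** covers an M1 lesion seen by the blinded reader but not by the site, or seen by the site without histology or confirmatory imaging: "then only conventional imaging at baseline will be used to determine the SoT".

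**Protocol 5.2** states both endpoints as percentages of patients, with no testing condition. SAP section 1 says that the SAP prevails where the two documents differ.

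**SAP 4.14.3.3** computes the N1 PPV in the EEP. The numerator needs histopathology; the denominator is every patient with a PET-positive pelvic node.

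**The concern.** The lead-in is the sentence that names the analysis set, and a programmer would normally build the denominator from it. Applied literally, it empties the two SoT-not-done cells that the formula provides for. It also removes patients whose truth comes from baseline imaging alone, and the numerator sentence has the same gap.

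Confirmation is requested for PET-positive M1 lesions (SAP 4.10), so untested patients are likely to be mostly BIE-negative, and these make up the bulk of a detection-rate denominator. Without them the figure no longer describes all scanned patients. Because the SAP prevails over the protocol, the protocol's wording does not settle the matter formally.

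A smaller issue of the same kind sits in 4.14.3.3. A PET-N1 patient who has no PLND enters the N1 PPV denominator but cannot enter the numerator, and the section does not say so.

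**Working it through.** **Plan figures.** The documents give no expected VDR or PPV, so there is no stated figure to reproduce for these endpoints. The only design calculation, 90% power for each co-primary test, reproduces at 90.4% (75 positive cases) and 90.6% (225 negative cases). This point does not depend on it.

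**Step 1. Who is counted under each statement of 4.14.3.1**

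| Patient | Lead-in alone | Lead-in plus sentence on unverified M1 | Formula |
|---|---|---|---|
| BIE M1, tested, SoT positive | in | in | TP |
| BIE M1, tested, SoT negative | in | in | FP |
| BIE M1, baseline imaging the only SoT, positive | out | in, as not verified | TP |
| BIE M1, baseline imaging the only SoT, negative | out | in, as not verified | FP |
| BIE M1, no SoT | out | in, as not verified | FP |
| BIE negative, tested | in | in | TN or FN |
| BIE negative, no SoT | out | out | TN |

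'Tested' means biopsy or additional imaging. The sentence on unverified M1 repairs the lead-in only for BIE-positive patients. BIE-negative patients without SoT are restored by the TN cell alone. For 4.14.3.2 the same table applies within the EEP patients whose conventional imaging was negative for M1.

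**Step 2. Effect on the rate.** Let N be the formula's denominator, t the share of N in the restricted set, and s the share of all TPs in that set.

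- Formula: TP/N
- Lead-in: s·TP/(t·N)
- Ratio of lead-in to formula: s/t

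The lead-in raises the rate whenever s exceeds t. That is to be expected, because confirmation is directed at PET-positive lesions. The ratio reaches 1/t only if every TP was tested (s = 1). Any TP resting on baseline imaging alone lowers it.

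**Step 3. Illustration only.** All inputs are assumed: EEP = 375 (planned enrolment, counted at consent, so the real EEP may be smaller), 60% of tested patients confirmed, s = 1.

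| Tested | TP | Formula | Lead-in | Ratio |
|---|---|---|---|---|
| 25 | 15 | 15/375 = 4.0% | 15/25 = 60% | 15 |
| 40 | 24 | 24/375 = 6.4% | 24/40 = 60% | 9.4 |
| 75 | 45 | 45/375 = 12.0% | 45/75 = 60% | 5 |

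In the middle row, adding 10 or 20 unverified BIE-M1 patients to the restricted set gives 24/50 = 48% or 24/60 = 40%.

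**Step 4. N1 PPV in 4.14.3.3.** Planning inputs (SAP 4.16) give TP = 75 × 0.40 = 30 and FP = 225 × 0.10 = 22.5, so PPV among operated patients = 30/52.5 = 57.1%. This uses the primary patient-level classification. If a share u of PET-N1 patients has no PLND, the EEP figure is 57.1% × (1 − u). The documents do not give u. Two assumed sets:

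- 25, 50 or 75 scanned patients without PLND, with PET-N1 as common as in the plan (52.5/300 = 17.5%), add 4.375, 8.75 or 13.125 to the denominator. The result is 52.7%, 49.0% or 45.7%.
- 15, 30 or 45 PET-N1 patients without PLND give 30/67.5 = 44.4%, 30/82.5 = 36.4% or 30/97.5 = 30.8%.

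The spread shows that the documents fix only the direction.

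**The case against.** The strongest reply is that 4.14.3.1 resolves itself. The formula is explicit, it names the EEP, and its cells provide for SoT not done. SAP 4.5 assigns M1 efficacy to the EEP. An additional EEP table, by reader, of BIE-M1 patients with and without confirmation would help expose a wrong denominator. This stands, and it makes the point minor. It does not make the lead-in harmless: two subsections still name a set that the formula contradicts, and the numerator sentence conflicts with 4.12 item 3 even if the formula is followed.

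A reader might infer three stronger claims that the documents do not support.

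- **The VDR would be inflated by a known multiple.** The ratios in the illustration rest on an assumed tested share and on all TPs being tested. The second assumption fails if any TP rests on baseline imaging alone.
- **The VDR would become the M1 PPV.** That needs unverified BIE-M1 patients kept and no BIE-negative patient tested. Local reads guide confirmation (protocol 9.1.6), so a patient called M1 by the site but not by the blinded reader would be asked to have confirmation.
- **The N1 PPV is wrong, or is a worst-case bound.** The EEP rule is written out, and it fits the SAP's practice of scoring unverified positives against the product (4.14.1.2, 4.14.3.1, 4.14.3.4). A per-reader PPV in the Efficacy Analysis Population (EAP) is already planned (4.14 and 4.14.1). Nor is the figure a strict lower bound: 4.14.3.3 states no same-side matching, so a patient PET-positive on one side and pathology-positive only on the other might count as confirmed.

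**Conclusion.** The concern holds as a minor drafting conflict. The lead-ins of 4.14.3.1 and 4.14.3.2 cannot be reconciled with the definitions below them, and the lead-in and numerator sentence omit the baseline-imaging-only SoT that 4.12 item 3 and the note in the FP cell count. The formula is the likely operative rule and agrees with the protocol endpoints. If the lead-in were programmed instead, the VDR would be inflated, assuming that TPs are over-represented among tested patients; the documents do not give the size.

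For the N1 PPV, only a label and a count are missing. The EEP figure is lowered by PET-N1 patients who were never verified, by an amount the documents do not fix. These secondary endpoints are descriptive (SAP 4.14.3). The co-primary tests, their error rate and the sample size are unaffected.

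**What to change.** 1. In the lead-ins of 4.14.3.1 and 4.14.3.2, delete the confirmation-tested condition with its bracket. The denominators are then all EEP patients (endpoint 1) and EEP patients with conventional imaging negative for M1 by investigator assessment (endpoint 2).
2. In the numerator sentence of 4.14.3.1, replace the bracket naming biopsy and additional imaging with confirmation by SoT under Section 4.12, at the same location.
3. Reword the sentence on unverified patients: BIE-M1 patients without verification are scored FP; BIE-negative patients without SoT are scored TN; where baseline conventional imaging is the only source, SoT follows 4.12 item 3.
4. In 4.14.3.3, add a footnote that the EEP N1 PPV counts PET-N1 patients without PLND as not confirmed. Report their number per reader, and refer to the EAP PPV planned in 4.14.1 as the figure among operated patients. Do not label the EEP figure a worst-case bound unless same-side matching is also specified.

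The cost is wording in three SAP subsections, one table footnote and one count row per reader. No new data are needed.

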Various retrospective studies have evaluated the utility of bone scans as a staging tool, with an incidence of bone metastases ranging from 3.5% (Ito, 2013) or 6.4% (De Nunzio, 2013) up to 20% (Chong, 2014) reported in patients with intermediate- and high-risk PCa. A false-positive rate of these bone scans of 20% has been reported (Chong, 2014), with MRI proving no better at detecting bone metastases. Specifically, a recent publication highlights the low probability of finding bone metastases on a staging MRI of the pelvis, with bone metastases identified in only 1.5% (57 of 3765) of cases and only in those with intermediate- and high-risk PCa (Vargas, 2017).

In the absence of confirmed M1 disease, PLND at the time of RP is recommended to assess for nodal disease and predict patient outcome (Moschini, 2016; Swanson, 2006). Furthermore, in cases where disease is limited to the prostate and regional lymph nodes (LNs; N1 disease), removal of regional LN metastases is performed with curative intent. Similarly, diagnosis of M1 disease beyond the field of surgery or radiotherapy allows both the patient and clinician to make more informed decisions about appropriate adjuvant, often systemic, treatments (Roach, 2018). Several methods to predict the absence or presence of M1 disease have been used with limited success, including nomograms, CT, MRI and PET imaging (Cagiannos, 2003; Schiavina, 2008; Park, 2015; Zarzour, 2017).

With respect to the detection of N1 disease, a recent meta-analysis of 24 studies including 2928 patients demonstrated a pooled overall sensitivity of MRI for the detection of LN metastases of only 56% (Woo, 2018). PET using ¹¹C-choline did not perform materially better, with a sensitivity of 59% for the detection of LN metastases (Huang, 2018). A variety

of studies have recently evaluated ⁶⁸Ga-PSMA-11 PET or ¹⁸F-DCFPyL PSMA PET as a decision-making aid in the prediction of N1 disease (Table 1). Although specificity was relatively high in these studies, the sensitivity compared to LN dissection and pathological examination was rather low, with point estimates ranging from 31% to 71%.

Table 1: Evaluation of ⁶⁸Ga-PSMA-11 PET and ¹⁸F-DCFPyL PSMA PET in N1 Disease

Tracer	Study	Sensitivity	Specificity	No. Patients
⁶⁸ Ga-PSMA	van Kalmthout, 2019 ; prospective, controlled study	42% (27% to 58%) ^a	91% (79% to 97%) ^a	96
⁶⁸ Ga-PSMA	Pooled analysis of four studies (Von Eyben, 2018)	61% (47% to 72%) ^a	97% (85% to 99%) ^a	224

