9.1 Clinical Assessments**9.1.1 *Concomitant Medications***

All concomitant medication and concurrent therapies will be documented at screening, with any changes in concomitant medication during the study recorded on the eCRF. The dose, route, unit frequency of administration, and indication for administration and dates of medication will be captured.

9.1.2 *Demographics*

Demographic information (full/partial date of birth/age, gender, ethnicity/race, sex, height, weight, as permitted by local regulations) will be recorded at screening. Weight will also be recorded pre-IP administration on the day of the rhPSMA-7.3 (¹⁸F) injection.

9.1.3 *Medical History*

Relevant medical history, including history of current disease, concomitant disease record, information regarding underlying diseases will be recorded at screening. Histological confirmation of adenocarcinoma of the prostate must be provided at screening.

If not already performed within 60 days prior to screening, conventional imaging as part of routine clinical practice, which may include bone scan (^{99m}technetium-hydroxydiphosphate [^{99m}Tc-HDP], ^{99m}technetium-methyldiphosphonate [^{99m}Tc-MDP]), abdominal/pelvic CT or MRI, and chest CT as per local practice) will be performed. Conventional imaging that has been performed at non-participating institutions will be accepted provided the scans are retrievable and reviewed by the participating institution.

Note: baseline conventional imaging performed as part of routine clinical practice should be performed at least 24 hours prior to the investigational rhPSMA-7.3 (¹⁸F) PET scan.

9.1.4 *Physical Examination*

A focused physical examination will be performed by an appropriately licensed and credentialed clinician at screening and at the safety follow-up visit within 1 to 3 days post-IP administration (may occur within 1 to 5 days post-IP administration due to the COVID-19 pandemic). New abnormal physical exam findings must be documented on the eCRF. Any clinically significant changes (as determined by the site investigator) in physical examination findings should be reported as an AE.

9.1.5 *Vital Signs*

Vital signs (body temperature, blood pressure, pulse and respiration rates) will be recorded after resting for 5 minutes at screening and pre- and post-IP administration on the day of rhPSMA-7.3 (¹⁸F) injection.

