10.3 Visit 1 and Visit 2 combined (Day 1; IP Administration)

Due to the COVID-19 pandemic, for patients who already have baseline conventional imaging, Visit 1 and Visit 2 may be combined (named “Visit 1 and Visit 2 combined”) if judged by the investigator to be necessary to decrease potential exposure to severe acute respiratory syndrome coronavirus 2 (SARS-CoV-2) for patients.

If Visit 1 and Visit 2 are combined, please complete all the procedures listed under Visit 1 and Visit 2 ([Sections 10.1](#) and [10.2](#), respectively) after obtaining written informed consent. Omit those procedures identified as not being required if combining visits.

Notes: Visit 1 and Visit 2 combined requires pre-screening via telephone contact prior to Day 1 to review the study eligibility criteria, obtain initial consent (remote consent is acceptable if permitted under local regulations and approvals), to promote study visit compliance and to ensure patient understanding of the combined study visit and planned IP administration, as well as ask about baseline conventional imaging that may already have been performed or needs to be scheduled (note the specified requirement regarding bone scans [[Section 10.1](#)]).

At sites where IP is not manufactured on-site, IP should be ordered prospectively at least 5 days in advance in accordance with the IP Supply Manual.

For sites with on-site manufacturing, the visits may be combined if mutually agreed by the Radiopharmacy and investigator even post-COVID-19 pandemic restrictions.

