4.6.2 Baseline conventional imaging

Baseline conventional imaging will be taken from imaging performed within the 60 days before screening or will be performed prior to IP administration.

The imaging results classified as baseline (above) will be summarized using FAS, EAP, EEP and PP by imaging modality and as positive or negative for detection of N1 or M1 disease. Patients with more than one baseline scan will be summarized for the combination of baseline scans and include all applicable anatomical areas covered. A listing will contain all these baseline parameters and include the imaging modality (CT, MRI, bone Scan, etc).

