4.14.3.6 Upstaging

- a) The percentage of patients being upstaged to N1 or M1 disease;*
- b) The percentage of patients in whom planned RP is converted to EBRT.*

The endpoints will be calculated as follows:

- Upstaging to N1 = Proportion of patients with positive BIE PET finding by BIE and negative conventional imaging finding from local investigator in pelvic lymph nodes, out of all the patients with evaluable scans.
- Upstaging to M1 = Proportion of patients with positive BIE PET finding and negative conventional imaging finding from local investigator in other (extra-pelvic) areas, out of all the patients with evaluable scans.

PAREXEL International

Blue Earth Diagnostics
BED-PSMA-301

Statistical Analysis Plan

- Planned RP converted to EBRT = Proportion of patients with positive BIE PET finding and planned RP changed to EBRT by local investigator, out of all the patients with evaluable scans.

4.14.3.7 Kappa statistic for the agreement between and within blinded independent readers on the interpretation of rhPSMA-7.3 (¹⁸F) scans.

This analysis concerns all EEP patients.

For this analysis, the patient's categorization to positive or negative by the blinded readers will be used, in pelvic lymph nodes and in extra-pelvic region.

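### The conventional-negative M1 detection rate and M1 upstaging set no rule on which body areas baseline imaging must have covered, so PET lesions in unscanned areas can count as M1 that conventional imaging missed.

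*SAP*

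**What the plan says.** **Endpoint 2 (SAP 4.14.3.2).** The rate is one "where both the numerator and denominator are only counting patients with negative conventional imaging (according to investigator assessment) for M1 disease". The numerator is men "with negative conventional imaging (according to investigator assessment) for M1 disease and with True-Positive M1 disease according to rhPSMA-7.3" PET. No modality or body area is required.

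**M1 upstaging (SAP 4.14.3.6).** The definition reads: "Upstaging to M1 = Proportion of patients with positive BIE PET finding and negative conventional imaging finding from local investigator in other (extra-pelvic) areas". The denominator is all men with evaluable scans. Unlike endpoint 2, the PET finding need not be verified.

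**What the imaging is.** Protocol 9.1.3 asks for "conventional imaging as part of routine clinical practice, which may include bone scan" and "abdominal/pelvic CT or MRI, and chest CT as per local practice". Protocol 10.1 uses the same permissive wording. Protocol Section 2 notes that guidelines recommend bone and abdominal/pelvic imaging for high- and very high-risk men, but for only a subgroup of unfavorable intermediate-risk men, who are also eligible here.

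**How it is recorded.** SAP 4.6.2 summarizes baseline imaging "by imaging modality and as positive or negative for detection of N1 or M1 disease". It also reports the anatomical areas covered when a man has several scans, and lists modality. It has no level for an area that was not imaged, and no endpoint definition uses the coverage information.

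**Where PET can score M1, and how it is verified.** SAP 4.14.3.1 allows M1 in nodes outside the pelvis, soft tissue or bone. It requires the confirmation to be at the same location as the PET lesion. SAP 4.12 item 2a accepts an unequivocal positive bone scan as proof.

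**The concern.** Endpoint 2 and M1 upstaging will be read as what PET adds once conventional imaging has come back negative. With no coverage rule, that quantity is mixed with another: what is found by imaging an area nobody had yet imaged.

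Take a man whose only baseline scan is an abdominal/pelvic CT, called negative for M1. PET shows a lesion in an upper rib, outside the field of that CT. A first bone scan is then done as confirmatory imaging and is positive at the same rib. Under the SAP he can be a verified M1 in a conventional-negative man, and can also count as upstaged to M1. Yet the only conventional test that looked at the rib was positive.

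At stake is the interpretation of two secondary results, and their comparability across sites and risk groups whose local imaging practice differs.

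**Working it through.** The documents give no expected value for either rate, so there is no figure to reproduce. The check covers direction, weight per man, and an illustration.

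**1. Direction.** Let A be the men counted under the SAP rule. Let B be those in A with at least one counted lesion in an area that a suitable baseline scan covered and called negative. B is a subset of A. With the same denominator N, |A|/N ≥ |B|/N. The SAP rate is therefore equal or higher, never lower. This holds for both endpoints.

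**2. Weight per man.** Protocol 4.1 plans up to about 375 enrolled and at least 300 evaluable.
- 1/375 = 0.27 percentage points.
- 1/300 = 0.33 percentage points.

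Endpoint 2 uses only conventional-negative men, so its N cannot exceed the enrolled number. At the planned enrolment of about 375, 0.27 is close to the least that one man can add.

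**3. Illustration for endpoint 2.** Three inputs are assumptions, because the documents give none of them:
- u = share of conventional-negative men with at least one M1-relevant area not imaged;
- v = detection rate counting only lesions in imaged areas, taken as equal in both groups;
- e = further verified M1, among the men in u, found only in unimaged areas.

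SAP rate = (1 − u)·v + u·(v + e) = v + u·e.

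| u | v | e | SAP rate | Excess | Ratio to v |
|---|---|---|---|---|---|
| 10% | 8% | 2 points | 8.2% | 0.2 points | 1.03 |
| 25% | 5% | 5 points | 6.25% | 1.25 points | 1.25 |
| 50% | 3% | 5 points | 5.5% | 2.5 points | 1.83 |
| 0% | any | any | v | 0 | 1.00 |

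The first and third rows are the extremes of the grid u = 10–50%, v = 3–8%, e = 2–5 points.

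**4. Restricting to fully imaged men is a different comparison.** The denominator then changes too. Suppose fully imaged men have a rate of 5%, and the 25% who are less fully imaged have a rate 2 points lower, for instance because they are at lower risk. The rate in all conventional-negative men is 0.75 × 5% + 0.25 × 3% = 4.5%. Restriction would raise it to 5%. The direction in step 1 does not carry over.

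**5. Which endpoint is more exposed.** Under SAP 4.14.3.1, a PET-positive man whose M1 is not proven is a false positive, so an unverified lesion in an unscanned area does not enter endpoint 2. Upstaging has no such filter.

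**The case against.** **The plan may intend the actual work-up.** Conventional imaging is described as routine practice, and secondary objective 6 is about impact on men planned for RP. A man planned for surgery on whatever work-up he had, then found to have M1, has in that sense been upstaged. This is a legitimate quantity and a reason to keep the current definition on display. It does not show how much of the result comes from lesions that conventional imaging looked at and missed.

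**No text says that an unscanned area is recorded as negative.** True. The rule is the investigator's assessment, and the eCRF and imaging review documents listed in SAP Section 1 are not available here. They might define coverage. This limits the claim to what the SAP allows, not what will happen.

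**Upstaging refers to extra-pelvic areas.** A man with only a pelvic MRI arguably has no extra-pelvic finding and falls outside SAP 4.14.3.6. That stands. But the category pools all extra-pelvic sites, so a negative abdominal scan can still be paired with a lesion in an unscanned chest or skeleton.

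**A dropped bone-scan requirement?** Protocol 10.3 says "note the specified requirement regarding bone scans" and points to 10.1, and a reader might infer that a mandatory scan was lost. The documents do not show this. Item 9 of 10.1 sets conditions for conventional imaging, bone scan included: a 60-day window before screening, completion at least 24 hours before PET, and review of outside scans. The cross-reference has a plausible target.

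**A larger size?** A reader might multiply an assumed unscanned share by the bone-metastasis incidences in Protocol Section 2 (3.5% to 20%). The share is not given, and those incidences come from men who had bone scans. Men without bone imaging may be at lower risk. The source of the 20% incidence is also cited for a 20% bone-scan false-positive rate. Not every such man would be PET-positive and verified. Likewise "bone metastases identified in only 1.5% (57 of 3765) of cases" on pelvic MRI is a yield, not a miss rate.

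**Conclusion.** The gap is real. Followed as written, the SAP can count a verified M1 lesion in an area no baseline scan covered towards endpoint 2, and a PET lesion in an unscanned extra-pelvic area as M1 upstaging. This rests on three features of the text: the work-up is optional, the definitions carry no coverage rule, and the only location match is between the PET lesion and its confirmation.

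The upward direction is certain only against a lesion-matched count with the same denominator. The size cannot be derived from the documents. It is zero with full coverage and about 0.27 points per man at N = 375. The 0.2 to 2.5 point range above depends wholly on assumed inputs. A reader might infer that limiting the analysis to fully imaged men must lower the rate, but that is not guaranteed.

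Both endpoints are secondary and descriptive, with no test or target. The co-primary sensitivity and specificity are untouched. The change is worth making before results are known.

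**What to change.** 1. **SAP 4.6.2:** code each extra-pelvic area (bone, extra-pelvic nodes, soft tissue) at baseline as positive, negative or not assessed. State beforehand which modalities count as suited to which tissue.
2. **SAP 4.14.3.2 and 4.14.3.6:** keep each denominator as it is. Count a man in the numerator only if a baseline scan suited to that tissue covered a PET-positive location (a verified one for endpoint 2) and was negative there. Report men counted only for lesions in not-assessed areas on a separate line. Do not remove PET-positive men with uncovered lesions from the denominator, because eligibility would then depend on the PET result.
3. **Supportive analysis:** repeat endpoint 2 in men whose baseline work-up included both bone imaging and abdominal/pelvic CT or MRI. This group is defined before PET. Note that the rate may move either way.
4. **Show the current SAP definition alongside.** The two lines in item 2 add up to it.

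The cost is SAP wording and programming. SAP 4.6.2 already plans to report modality and areas covered, though whether areas are captured finely enough depends on the eCRF. The lesion-matched rates may be lower than the current definition would give. No patient procedure changes.
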